5.1.2 Secondary Endpoints

- ORR, DOR, and DCR according to iRECIST and modified RECIST 1.1 (Dose Escalation part only)
- PK profile in plasma, urine, and feces (Dose Escalation part) and plasma only (in Dose Expansion part)
- PFS, defined as the time from the **date of first dose** to the date of the first documentation of qualified disease progression (see Section 5.4.2.4) or death, whichever occurs first
- OS, defined as the time from the date of first dose to the date of death from any cause
- Change in tumor size in injected lesions

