## **Dose Escalation part**

- Evaluate preliminary clinical activity of E7766 based on investigator assessment of ORR, DOR, and DCR according to modified RECIST 1.1 and iRECIST for solid tumors, and Lugano and LYRIC criteria for lymphoma
- Evaluate the pharmacokinetic (PK) profile of E7766 and any metabolites in plasma, urine, and feces

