# 9.7.1.1.2 SECONDARY ENDPOINTS

- ORR, DOR, and DCR according to iRECIST and modified RECIST 1.1, or Lugano and LYRIC (Dose Escalation part only)
- PK profile in plasma, urine, and feces (Dose Escalation part) and plasma only (in Dose Expansion part)
- PFS, defined as the time from the date of first dose to the date of the first documentation of confirmed disease progression or death, whichever occurs first
- OS, defined as the time from the date of first dose to the date of death from any cause
- Change in tumor size in injected lesions and in distant non-injected lesions

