3.1.2 Secondary Objectives

The secondary objectives of the study are:

Dose Escalation part

- Evaluate preliminary clinical activity of E7766 based on investigator assessment of ORR, DOR, and DCR according to modified RECIST 1.1 and iRECIST for solid tumors
- Evaluate the pharmacokinetic (PK) profile of E7766 and any metabolites in plasma, urine, and feces

Dose Escalation and Dose Expansion parts

- Evaluate the PK profile of E7766 and any metabolites in plasma

- Evaluate progression-free survival (PFS) based on investigator assessment and overall survival (OS) in subjects treated with E7766
- Evaluate tumor size changes per investigator assessment in injected lesions

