3.2 Overall Study Design and Plan

This is an open label, multicenter, Phase 1/1b study to assess the safety and evaluate the clinical activity of E7766 administered intratumorally to subjects with advanced solid tumors or lymphomas. A Dose Escalation part will enable selection of a dose of E7766 to move forward with as the RP2D in the Dose Expansion part, where clinical activity in selected tumor types or populations will also be evaluated.

Dose escalation will be conducted using an improved modified toxicity probability interval (i.e. mTPI-2) design (Guo et al., 2017; Yan et al., 2017) to determine the MTD for E7766. Each subject will be assessed for tumor response (injected and noninjected lesions), PK, and pharmacodynamics (blood and tumor factors). The RP2D will be selected based on integrating results of safety (including the MTD), clinical activity, PK, and pharmacodynamics. During the Dose Escalation part, selected dose level cohorts may accrue additional subjects to provide further safety, drug administration-related, biomarker, and/or PK data needed for selection of the RP2D. Intrapatient dose escalation of study drug will be allowed in the study.

The Dose Expansion part will be initiated when the RP2D and/or MTD is available from the Dose Escalation part. In the Dose Expansion part, separate study arms will evaluate E7766 at the RP2D in selected tumor types and populations to confirm safety and assess clinical activity. The study populations will be decided based on the emerging data from the Dose Escalation part.

The overall study design is shown in Figure 1.

CRC = colorectal cancer, HNSCC = head and neck squamous cell carcinoma, RP2D = recommended Phase 2 dose.

Figure 1 Study Schematic for Dose Escalation and Dose Expansion Parts

A fixed E7766 dose will be administered for each subject. There will be no adjustments for subject weight.

E7766 will be administered in cycles which are 3-weeks long, with treatment as follows:

- Induction (Cycle 1): injection on Days 1, 8, and 15
- Maintenance (Cycle 2 and after): injection on Day 1 of each cycle, once in 3 weeks (Q3W)

Approximately 35 to 40 subjects will be enrolled in the Dose Escalation part and 80 subjects will be enrolled in the Dose Expansion part.

The end of the study will be the date of data cutoff for the final analysis or last subject/last visit, whichever occurs later.

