5.1 Study Endpoints

5.1.1 Primary Endpoints

- Safety-related endpoints, including DLT
- ORR according to modified RECIST 1.1 and iRECIST, defined as the proportion of subjects achieving a best overall response (BOR, see Appendix **Error! Reference source not found.**) of confirmed partial response (PR) or complete response (CR). Subjects who do not have a tumor response assessment for any reason will be considered nonresponders and will be included in the denominator when calculating the response rate (Dose Expansion part only)
- DOR according to modified RECIST 1.1 and iRECIST, defined as the time from the date of first documented and **confirmed PR or CR** until the first documentation of qualified disease progression (see Section 5.4.2.4) or death, whichever occurs first (Dose Expansion part only)
- DCR according to modified RECIST 1.1 and iRECIST defined as the proportion of subjects achieving BOR as PR or CR or stable disease (SD) (Dose Expansion part only)

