5.2 Study Subjects

5.2.1 Definitions of Analysis Sets

DLT Analysis Set is the group of subjects in the Dose Escalation part who have completed Cycle 1, without incurring certain major protocol deviations (for instance those related to dosing or others identified before database lock), with at least 2 E7766 injections during Cycle 1, and are evaluable for DLT, or subjects who have experienced DLT during Cycle 1. This will be the analysis set to evaluate tolerability.

Full Analysis Set is the group of subjects who received at least 1 dose of study drug. This will be the primary analysis set for efficacy evaluations, as well as for demographic and baseline characteristics.

Safety Analysis Set is the same group as Full Analysis Set. This will be the analysis set for all safety evaluations except DLT results.

Efficacy Analysis Set is the group of subjects who received at least 1 dose of study drug and had a baseline tumor assessment. This will be used for supportive analysis of ORR.

Pharmacodynamic Analysis Set and Pharmacokinetic/Pharmacodynamic Analysis Set are defined in separate PK or PK/PD analysis plan(s).

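### The SAP drops Lugano and LYRIC from the Dose Escalation response and progression rules without explanation, while its stated population and Full Analysis Set still admit lymphoma

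*SAP*

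**What the plan says.** Protocol 8.2 sets the Dose Escalation response objective by tumor type: "modified RECIST 1.1 and iRECIST for solid tumors, and Lugano and LYRIC criteria for lymphoma". Protocol 9.7.1.1.2 carries this into the endpoint: "ORR, DOR, and DCR according to iRECIST and modified RECIST 1.1, or Lugano and LYRIC (Dose Escalation part only". Protocol 9.5.1.3.2 has lymphoma scanned at Week 9 and then every 12 weeks.

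The SAP repeats both statements without the lymphoma part. Its secondary objective (3.1.2) is "ORR, DOR, and DCR according to modified RECIST 1.1 and iRECIST for solid tumors" and its endpoint (5.1.2) is "ORR, DOR, and DCR according to iRECIST and modified RECIST 1.1 (Dose Escalation part only". In 5.4.2.4, qualified PD is defined for modified RECIST and for iRECIST only. The missed-assessment limit there is 97 days, justified by the 6-weekly solid-tumor scans.

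Other parts of the SAP keep lymphoma. Section 3.2 describes E7766 as "administered intratumorally to subjects with advanced solid tumors or lymphomas", and 3.1.1 does the same for the safety and MTD objectives. Section 5.2.1 states that the "Full Analysis Set is the group of subjects who received at least 1 dose of study drug", and 5.4 makes that set primary for efficacy. Section 7 lists six removed analyses; the lymphoma criteria are not among them. The list does include tumor assessment listings and the efficacy analysis on the Efficacy Analysis Set.

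**The concern.** Part of a protocol secondary objective, lymphoma ORR, DOR and DCR in Dose Escalation, has no analysis in the SAP, and no reason is given. The rules that remain do not fit a lymphoma subject who enters the Full Analysis Set. Such a subject is counted in a denominator whose numerator is defined by criteria the protocol does not apply to lymphoma, and progression cannot be classified.

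Expansion was cancelled (SAP 3.2.2), so Dose Escalation is the study's only source of efficacy data. Results are summarized by initial dose level, and cohorts start at two subjects, so a single subject can matter to what a dose level shows. Because Section 7 removes the tumor assessment listings, no planned tumor-assessment output would show a lymphoma response.

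**Working it through.** The documents state no figure for this point except the 97-day limit. The check is a comparison of texts, then the consequences for any lymphoma subject.

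1. **Response criteria.** Protocol 8.2 and 9.7.1.1.2 name RECIST/iRECIST for solid tumors and Lugano/LYRIC for lymphoma. SAP 3.1.2 and 5.1.2 name RECIST/iRECIST only. LYRIC survives only in the SAP's abbreviation list; Lugano does not appear in the SAP text available for review.

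2. **ORR and DCR.** Let N be the subjects treated, L those with lymphoma, x the solid-tumor responders and y the lymphoma responders. None of these is given.
   - SAP as written (RECIST/iRECIST numerator, Full Analysis Set denominator): x/N.
   - Protocol endpoint, each tumor type by its own criteria: (x + y)/N.
   - Solid tumors only: x/(N − L).
   - Since x/N = [x/(N − L)] × (N − L)/N, the written rule multiplies the solid-tumor rate by (N − L)/N. It falls short of the pooled protocol rate by y/N. With L = 0 all three agree.

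   The route to this denominator is SAP 5.4 (Full Analysis Set) together with 5.4.2.1, which gives escalation ORR the expansion method. It does not need the nonresponder sentence in 5.1.1. DCR follows the same arithmetic through 5.4.2.3. DOR uses confirmed responders only, so lymphoma responders would be absent from it.

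3. **Progression for PFS and DOR.** Qualified PD has no Lugano/LYRIC branch, and the iRECIST branch cannot stand in. SAP 5.4.2.4 requires confirmation 4 to 8 weeks after unconfirmed progression, whereas protocol 9.5.1.3.2 repeats lymphoma imaging after 12 weeks, or sooner if clinically indicated. Protocol Appendix Table 5 also dates a progression confirmed after an indeterminate response back to the indeterminate assessment, if no objective response intervened. The SAP does not carry this over. On scheduled re-imaging the two dates differ by about 12 × 7 = 84 days.

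4. **Missed-scan limit.** For solid tumors the SAP figure reproduces: 6 weeks = 42 days, window 7 days, 2 × (42 + 7) − 1 = 97. For lymphoma the interval is 12 × 7 = 84 days:
   - no scan missed: 84 days, within 97;
   - one 12-weekly scan missed: 2 × 84 = 168 days, beyond 97;
   - two missed: 3 × 84 = 252 days.

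   If the Week 9 scan is missed, the next falls at about day 63 + 84 = 147, also beyond 97. The SAP intends censoring after more than one missed assessment. If 97 days, the only limit given, were applied to lymphoma, one missed scan would be enough.

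**The case against.** The strongest reply is that the removal looks deliberate. The SAP text postdates the decision of 26 April 2022 not to open expansion, when the treated tumor types could have been known. Lymphoma response criteria are absent throughout its objectives, endpoints and PFS rules, and the 97-day note says it is for solid tumors. The population wording may simply be repeated protocol design text. This is plausible, and nothing in the documents refutes it. But Section 7 is where such a change belongs and does not mention it. The swimmer and waterfall plots are limited to solid-tumor subjects, while ORR, DOR, DCR and PFS are not.

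A reader might infer that lymphoma subjects were treated and that a Lugano complete response will be reported as a nonresponse. The documents do not support either as fact. No text shows that a lymphoma subject was treated. The sentence "Subjects who do not have a tumor response assessment for any reason will be considered nonresponders and will be included in the denominator" stands in a bullet labelled for Dose Expansion only, and 5.4.1.2, to which escalation ORR is referred, does not repeat it. It also concerns subjects with no tumor response assessment at all, and a subject assessed by Lugano has one. The wording of SAP 3.1.2 would even allow RECIST endpoints to be read as covering solid-tumor subjects only. What stands is narrower: the Full Analysis Set denominator is stated without restriction by tumor type.

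A reader might also divide by the planned 35 subjects to get a loss per lymphoma responder. That figure is not supportable: 35 is the anticipated size, escalation stopped early, and the number treated is not given. It would also assume a pooled ORR, which a solid-tumor-only denominator replaces.

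Two further points are fair. Efficacy is descriptive, with no comparisons and no primary efficacy analysis in escalation. Some derivations may also sit in table shells, dataset specifications or the best-overall-response appendix, whose cross-reference in 5.1.1 is broken.

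**Conclusion.** The conflict between protocol and SAP is real and unexplained. Its numerical effect is conditional. With no lymphoma subject treated, no result changes and the defect is one missing sentence. With L > 0, the ORR and DCR as written are the solid-tumor rates multiplied by (N − L)/N, lymphoma responses go unreported, lymphoma progression has no rule for PFS or DOR, and the 97-day limit, if used, is passed after one missed scan instead of two. This assumes that sites record lymphoma by Lugano/LYRIC only, as the protocol directs, and that separate specifications do not already resolve the matter. OS, DLT and safety analyses do not depend on these criteria. The lymphoma objective in Dose Expansion was conditional on lymphoma being included and is moot. The point should be settled before reporting, but it does not touch the study's main safety conclusions.

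**What to change.** If no lymphoma subject was treated, say so in SAP Section 7 as the reason for dropping Lugano/LYRIC. That costs one sentence.

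Otherwise:
- In SAP 5.1 and 5.4, restrict modified RECIST 1.1/iRECIST ORR, DCR and DOR to subjects with solid tumors.
- Report lymphoma subjects separately by Lugano/LYRIC in an individual listing, as an exception to Section 7's removal of tumor assessment listings.
- In 5.4.2.4, add a lymphoma definition of qualified PD, dated as in protocol Appendix Table 5.
- Add a missed-scan limit matched to Week 9 and then 12-weekly scans. It should exceed the 168-day gap left by one missed 12-weekly scan and stay below the 252 days left by two. The protocol gives no window for lymphoma scans. Assuming the 7-day solid-tumor window, the SAP's own construction gives 2 × (84 + 7) − 1 = 181 days.

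This costs a few SAP sentences and one listing, from data the protocol already collects. No new assessment is needed.

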#### **Efficacy Analyses**

Evaluation of clinical activity will be primarily performed on the Full Analysis Set. Summary of clinical activity on the Efficacy Analysis Set will also be provided as needed. Objective response rate (ORR), DOR, DCR, PFS, assessed by the investigator, and OS will be listed and descriptively summarized as appropriate. If applicable, a waterfall plot will be presented for the percent changes from baseline in the sum of the diameters of target lesions at post-baseline nadir (ie, maximum tumor shrinkage).

- **ORR** will be calculated with exact 95% CI using the Clopper and Pearson method. Summary of best overall response will also be presented.
- **DOR** will be summarized using Kaplan-Meier estimates as appropriate. Median, Q1, Q3, and their 95% CIs will be presented and Kaplan-Meier estimates will be plotted over time. The DOR will be based on subjects achieving a best overall response of confirmed PR + CR.
- DCR will be calculated with exact 95% CI using the Clopper and Pearson method.
- **PFS** will be summarized using Kaplan-Meier estimates. Median, Q1, Q3, and their 95% CIs will be presented and Kaplan-Meier estimates will be plotted over time. Subjects without progression of disease or death will be censored at the time of the last tumor assessment.

Eisai Confidential Page 26 of 138

• OS will be summarized using Kaplan-Meier estimates. Median, Q1, Q3, and their 95% CIs will be presented and Kaplan-Meier estimates will be plotted over time. Subjects who are lost to follow-up or withdrew consent will be censored at the last known alive date, or the data cutoff date, whichever occurs first. Subjects who remained alive will be censored at the time of data cutoff.

The analysis using the tumor assessment by lesions, such as injected lesions and non-injected lesions, will be collected and conducted separately. Time course changes in pre-injection size of injected lesion will also be provided separately.

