## **Dose Escalation and Dose Expansion parts**

- Evaluate the PK profile of E7766 and any metabolites in plasma
- Evaluate progression-free survival (PFS) based on investigator assessment and overall survival (OS) in subjects treated with E7766
- Evaluate tumor size changes per investigator assessment in injected lesions and in non-injected lesions

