# 9.7.1.6 Efficacy Analyses

Evaluations of clinical activity will be performed primarily on the Full Analysis Set. A summary of clinical activity on the Efficacy Analysis Set will also be provided as needed. The ORR, DOR, DCR, PFS (as assessed by the investigator), and OS will be listed and descriptively summarized as appropriate. If applicable, a waterfall plot will be presented for the percent changes from baseline in the sum of the diameters of target lesions at postbaseline nadir (ie, maximum tumor shrinkage). The summary will be presented for each dose level/arm, total of each part, and overall as appropriate.

The analysis using the tumor assessment by lesions, such as injected lesions and non-injected lesions, will be conducted separately for the selected efficacy endpoints, if appropriate.

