### 9.7.1.6.2 SECONDARY EFFICACY ANALYSES

- **ORR, DOR,** and **DCR** for the Dose Escalation part will be evaluated using same methodology for primary analysis in the Dose Expansion part.
- **PFS** will be summarized using Kaplan-Meier estimates. Median, Q1, Q3, and their 95% CIs will be presented and Kaplan-Meier estimates will be plotted over time. Subjects without progression of disease or death will be censored at the time of the last tumor assessment.
- OS will be summarized using Kaplan-Meier estimates. Median, Q1, Q3, and their 95% CIs will be presented and Kaplan-Meier estimates will be plotted over time. Subjects who are lost to follow-up or withdrew consent will be censored at the last known alive date, or the data cutoff date, whichever occurs first. Subjects who remained alive will be censored at the time of data cutoff.
- Change in tumor size in injected lesions and in distant non-injected lesions will be presented using plots, such as waterfall plots/spider plots, if appropriate.

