5.4.2.6 Change in Tumor Size in Injected Lesions

For subjects with solid tumors based on modified RECIST 1.1 and iRECIST (if appropriate) assessments, a waterfall plot will be presented for the maximum percent change from baseline

in injected lesions. If a subject has multiple lesions injected, the first injected lesion will be included.

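### The SAP limits the secondary endpoint on tumor size change to injected lesions; the protocol also names distant non-injected lesions, and SAP Section 7 does not declare the change

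*SAP*

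**What the plan says.** **Protocol.** The secondary objective for both study parts (Section 8.2) is: "Evaluate tumor size changes per investigator assessment in injected lesions and in non-injected lesions". The matching secondary endpoint (Section 9.7.1.1.2) is: "Change in tumor size in injected lesions and in distant non-injected lesions". Section 9.7.1.6.2 says that both "will be presented using plots, such as waterfall plots/spider plots, if appropriate". Section 9.7.1.6 adds that by-lesion analyses of the two groups "will be conducted separately for the selected efficacy endpoints, if appropriate". The synopsis, under Efficacy Analyses, plans the by-lesion analysis without that condition: assessments by lesion, "such as injected lesions and non-injected lesions, will be collected and conducted separately".

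**SAP.** The objective in 3.1.2 is "Evaluate tumor size changes per investigator assessment in injected lesions" and stops there. The endpoint in 5.1.2 is "Change in tumor size in injected lesions". Section 5.4.2.6 carries the same restriction in its title and specifies one waterfall plot of maximum percent change from baseline in injected lesions for subjects with solid tumors, with this rule: "If a subject has multiple lesions injected, the first injected lesion will be included". The design text in SAP 3.2 still says that both lesion groups are assessed for response. Section 7 records that no MTD was determined and that there is no expansion analysis, then lists six items removed for the abbreviated report. Non-injected lesions are not among them.

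**The concern.** Protocol 7.1.1 states a two-step hypothesis: injection activates a local immune response in the injected tumor, and an adaptive response then acts on tumors elsewhere. Protocol 7.2 rests part of the study rationale on nonclinical activity in distant, untreated tumors. Shrinkage of an injected lesion bears on the first step. Size change in lesions that were never injected bears directly on the second. The overall response measures (ORR, DCR, DOR, PFS) are determined per subject and are not split by injection status.

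The part that disappears between protocol and SAP is therefore the part closest to the systemic claim, and it was a stated secondary objective. Protocol 9.5.1.3.3 provides for measurement data on individual lesions and for recording which lesion is injected at each dose, so the comparison was planned for at data collection.

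**Working it through.** No arithmetic applies; the check is a comparison of texts.

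**Step 1: the two documents side by side.**

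| Element | Protocol | SAP |
|---|---|---|
| Secondary objective | 8.2: both lesion groups | 3.1.2: injected only |
| Secondary endpoint | 9.7.1.1.2: both | 5.1.2: injected only |
| Analysis | 9.7.1.6.2: plots of both, conditional | 5.4.2.6: one plot, first injected lesion |
| Declared change | not applicable | Section 7: none of six items |

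The protocol names two lesion groups and the SAP one. The narrowing is the same in the SAP's objective, endpoint, section title and method, so it is not an artefact of text extraction.

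**Step 2: could another SAP analysis supply the missing group?**

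- ORR, DCR, DOR and PFS (5.4.1.2 to 5.4.2.4) use overall response and do not separate lesions by injection status.
- The volumetric endpoint (5.1.3) is not split by injection status and has no specified analysis.
- The pre-injection size endpoint (5.1.3) concerns injected lesions only.
- Section 5.7 plans nothing further. Sections 5.3.4 and 5.8 say only that subgroup or exploratory analyses may be done.
- The injected-lesion plot in 5.4.2.6 is the only waterfall the SAP specifies.
- Section 7 removes the tumor assessment listings, so a reader of the abbreviated report cannot count on them to recover lesion-level results.

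The number of specified SAP analyses that isolate non-injected lesions is zero.

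**Step 3: what limits the conclusion.** SAP Sections 5 and 11 refer to separate table, figure and listing shells, which are not available here. The result applies to what the SAP specifies and does not show what will finally be produced.

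**The case against.** The best case for the SAP is that the protocol allowed discretion. Sections 9.7.1.6 and 9.7.1.6.2 make the by-lesion analyses and plots conditional on being appropriate. The study stopped before expansion, the report is abbreviated, no statistical comparisons are planned (SAP 5.3.3), and Inclusion Criterion 5 asks for a second measurable lesion only where one is available. A plot with very few subjects could reasonably be left out.

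That argument covers the plot. It does not cover the objective or the endpoint, which carry no such condition in the protocol and which the SAP rewrote. A judgement that the plot is not worthwhile should be written down.

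Three stronger readings are tempting and are not supported.

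- *That the omission was hidden.* Five of the six Section 7 items are analyses still described in the SAP body, so the list reads mainly as cuts from that body and not as a full comparison with the protocol. This is a gap in documentation; nothing shows intent.
- *That the protocol contradicts itself*, because Section 9.5.1.3.3 calls the effect on injected versus non-injected lesions exploratory. That wording describes a contrast between groups. An exploratory contrast can coexist with a secondary endpoint describing size change in each group.
- *That the loss can be quantified*, for example as distant growth masked by shrinkage of the injected lesion. The documents give no lesion sizes to calculate from. The retained plot still shows the first injected lesion, and new lesions or unequivocal non-target progression count as progression anyway (Protocol Appendix 2).

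**Conclusion.** The point holds as an undeclared conflict between the protocol and the SAP that should be fixed. Followed as written, the SAP leaves half of a stated secondary objective unreported.

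The consequence is confined to descriptive reporting. A reader might infer that dose selection suffers, because Protocol 9.1.1.3 takes antitumor activity into account for the RP2D. The documents do not support that: the assignment rule uses DLTs only (SAP 5.3.6), no dose criterion refers to non-injected lesions, no MTD was determined (SAP Section 7), and no subjects will enter expansion (SAP 3.2.2).

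The conclusion assumes that the unseen shells do not already contain a figure for non-injected lesions. If they do, the reporting gap closes, but the SAP's objective, endpoint and analysis text would still disagree with the protocol. The practical value of the missing result depends on how many subjects have a serially measured non-injected lesion, which neither document states.

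**What to change.** 1. Restore distant non-injected lesions alongside injected lesions in SAP 3.1.2, 5.1.2 and 5.4.2.6.
2. Add a descriptive waterfall or spider plot of percent change from baseline in non-injected lesions, by initial dose level, with the number of subjects contributing. Keep the existing plot of the first injected lesion.
3. Restrict the new plot to lesions with serial measurements. Non-target lesions are followed qualitatively (Protocol Appendix 2), and skin lesions without photographic and measurement documentation are classed as non-target (Protocol 9.5.1.3.1).
4. End a lesion's series at its first injection, because Protocol 9.4.1.3 lets injection move to another lesion. Neither document contains this analysis rule; it is proposed here so that the group stays truly non-injected. Flag biopsied lesions, which Protocol 9.5.1.3.3 requires to be recorded.
5. If too few subjects have a measured non-injected lesion, report the count and declare the removal with its reason in Section 7.

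The cost is a few lines of SAP text and one or two descriptive figures from lesion data that the protocol already has collected. No new assessments are needed.
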